# 2. Outcome Measures

52	2.1. Primary outcome measure:
53	The primary outcome measure is patient reported pain on a numeric rating scale (NRS) (1; no
54	pain, 10; worst pain imaginable)
55	
56	2.2. Secondary outcome measures:
57	Patient satisfaction measured on NRS scale of 1=not bad at all, to 10=worst experience
58	imaginable.
59	Analysis of risk factors associated with pain from local anaesthetic in the head and neck
60	including size of resection and injection volume:
61	• Pathology – malignant versus benign
62	Local anaesthetic volume
63	• Size of resection
64	• Site of resection
65	
66	
67	3. Methodological design
68	3.1. Study design
69	Randomized controlled trial
70	
71	3.2. Selection:
72	Patients will be selected from those attending scheduled excision of cutaneous head and neck
73	malignancies at our centre
74	
75	3.3. Inclusion criteria:

76	• Aged at least 18 years
77	• Receiving surgery to cutaneous tissues of the head and neck
78	Procedure performed under local anaesthetic
79	
80	3.4. Exclusion criteria:
81	Paediatric patients
82	• Surgery performed under general anaesthetic
83	• Mucosal operative site (e.g. oral cavity)
84	• Significant cognitive impairment (e.g. severe dementia)
85	Known sensitivity/allergy to EMLA
86	• History of a pain disorder (e.g. complex regional pain syndrome).
87	
88	3.5. Sample size calculation:
89	A formal sample size calculation will be performed after an initial pilot study of ten patients
90	per group to calculate the effect size. Other studies on using topical anaesthetic agents in
91	other non head and neck anatomical sites typically required less than 50 participants per
92	group. G*Power 3.1 (Universität Düsseldorf) software will be used to calculate the necessary
93	sample size. We will likely employ an $\alpha$ error probability of 0.05 and a power of 95%. A 10%
94	margin for safety will be used to mitigate the possible risks of participant attrition
95	
96	3.6. Randomization:
97	Computer randomization will be performed. A random number sequence will be generated
98	using randomizer.org® with numbers allocated using stratified permuted blocks of four and
99	these will be concealed in individual sealed envelopes with the aid of a research contributor.

100	Participants will be allocated in order of recruitment and in participants with more than two
101	lesions will have the more superiorly located lesion allocated first.
102	

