103	3.7. Interventions
104	Patients will be split into 4 groups:
105	• EMLA
106	Aqueous ointment
107	• Ethyl chloride spray
108	• no treatment.
109	
110	3.8. Study procedures
111	Written informed consent will be obtained prior to group allocation. Following group
112	allocation, topical agents will be administered as follows. EMLA (EMLA cream 5% 25g
113	lidocaine, 25g prilocaine) and aqueous cream will be applied to cover the surgical site,
114	delivered via an unmarked syringe to achieve single blinding. A Tegaderm® adhesive
115	dressing will then be applied over this to prevent the cream from drying out, and it will be
116	removed in the theatre before the administration of LA. The local anesthetic to be used will
117	be 1% lidocaine with 1:200,000 adrenaline and will be injected via a 25-gauge needle
118	attached to a 10ml syringe. A 5ml syringe will be occasionally used when it is not possible to
119	inject via a 10ml syringe.
120	EC will be applied to the surgical site before LA injection. The area will be sprayed at a
121	distance of 5-10cm for 4-8 seconds until the skin slightly blanches, and the fluid will be
122	allowed to evaporate.

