### 126 **3.9.**Assessing outcomes

The key focus in this study will be the assessment of pain linked to the injection of local anesthesia (LA). Following the LA administration, each participant will be prompted to evaluate the pain they undergo using a numeric rating scale (NRS; 1=no pain, 10=worst pain imaginable). Subsequent to the procedure, patients will be inquired about their overall perception of the experience (1=not bad at all, 10=worst experience imaginable).

132

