## 133 4. Statistical analysis

The distribution pattern of variables will be assessed using the Kolmogorov-Smirnov test. 134 The Kruskal-Wallis test and Mann Whitney test will be employed to compare groups for non-135 parametric data and for covariate analysis. The Chi-squared test will be applied to detect 136 differences for categorical data. Spearman's Rho will be used to quantify the strength of the 137 138 linear relationship between non-parametric continuous variables. A per protocol analysis will be conducted as it is believed that in cases where patients are unable to describe their pain by 139 using a number, it will disproportionately affect the results by conducting a "worst case 140 141 scenario" analysis. Furthermore, due to a minimal interval between intervention and measurement of pain outcomes in this study, there will be low rates of attrition. Statistical 142 analysis will be performed using SPSS v.26 (Aramonk, US). Statistical significance will be 143 144 considered at p < 0.05.

145

- 146
- 147
- 148

149

150	5. Miscellaneous
151	5.1. Ethical considerations:
152	This trial will be registered with the University Hospital Waterford Research and Ethics
153	Committee where full ethical approval will be obtained prior to study commencement. It
154	is considered that patient risks from this study are negligible.
155	
156	5.2. Funding:
157	No funding will be necessary for this study
158	
159	5.3. Dissemination of results
160	Results will be prepared into a scientific manuscript for publication and presented at

161 scientific surgical meetings

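### Section 3.6 randomises within strata and can allocate several lesions from one participant, but the group tests in section 4 ignore both, so the primary test is not assured its 5% level

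*Combined protocol and SAP*

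**What the plan says.** Section 3.6 describes computer randomisation "with numbers allocated using stratified permuted blocks of four and" sealed envelopes. No stratification factor is named there or elsewhere. The same section continues: "Participants will be allocated in order of recruitment and in participants with more than two" "lesions will have the more superiorly located lesion allocated first". A rule for which lesion is allocated first implies that one participant can supply more than one allocated lesion. Read literally, the rule does not cover a participant with exactly two.

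Other sections speak of people rather than lesions. Section 3.7 says "Patients will be split into 4 groups", and in section 3.9 "each participant will be prompted to evaluate the pain they undergo". Section 3.5 also counts participants per group. It gives a likely alpha of 0.05 and power of 95%, and leaves the sample size to be calculated after a pilot.

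Section 4 says "The Kruskal-Wallis test and Mann Whitney test will be employed to compare groups" for data that are not normally distributed, and gives the same tests the covariate analysis. Chi-squared and Spearman complete the list, with significance at p < 0.05. The section mentions no stratified test, regression model, method for correlated observations or restriction to one lesion per patient.

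**The concern.** A test should reflect how the trial was randomised. Blocking within strata balances the arms on the stratum. If the stratum predicts pain, the arm means then vary less by chance than an unstratified test assumes, so that test rejects too seldom and wastes some of the precision that stratifying provides.

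Repeated lesions raise a separate problem. Two pain scores from one person are likely to be correlated, and Kruskal-Wallis and Mann-Whitney assume that they are not. The direction of the error depends on how those lesions are allocated. If they are allocated separately, they tend to fall in different arms within a block, part of the person effect cancels, and the test is conservative. If they share an arm, the effective sample size is smaller than the count of lesions and the test is anti-conservative.

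At stake is whether the declared 5% is the real level of the primary comparison. If the unit and strata stay unstated, they could also be settled after the data are seen.

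**Working it through.** **Inputs from the plan.** Four arms, blocks of four, significance level 0.05, power 95% (section 3.5, as likely values). The plan states no sample size, effect size, strata, share of patients with several lesions or within-patient correlation (ICC), so there is no figure of its own to reproduce. Those quantities are assumptions below. Pain is simulated as a rounded normal score limited to 1 to 10.

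**1. Strata ignored.** Let R² be the share of pain variance that the strata explain. Under stratified blocking the Kruskal-Wallis statistic behaves approximately as (1 − R²) times a chi-squared variable on 3 degrees of freedom. The 5% critical value is 7.815, so the true level is P(χ²₃ > 7.815/(1 − R²)).

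| R² | 7.815/(1 − R²) | Level by formula | Simulated (N = 48, 128, 192) |
|---|---|---|---|
| 0 | 7.815 | 5.0% | 4.7–5.1% |
| 0.1 | 8.683 | 3.4% | 3.1–3.5% |
| 0.2 | 9.769 | 2.1% | 1.8–2.3% |
| 0.3 | 11.164 | 1.1% | 1.1–1.2% |

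In the same simulations (6,000 null trials per cell), a rank model containing the stratum held 4.8–5.6%, and the van Elteren test held 4.4–5.4%.

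Power at N = 192, with an assumed shift of 0.62 SD in two arms, chosen to give about 95% at R² = 0 (3,000 trials per cell):

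| R² | Kruskal-Wallis | Stratum-adjusted | Gain (points) |
|---|---|---|---|
| 0 | 94.9% | 95.0% | 0.1 |
| 0.1 | 95.1% | 96.6% | 1.5 |
| 0.2 | 95.8% | 98.4% | 2.6 |
| 0.3 | 96.7% | 99.2% | 2.5 |

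For one pairwise comparison at R² = 0, Mann-Whitney has 82.6% and van Elteren 82.0%, a cost of 0.6 point if the strata carry no information.

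**2. Repeated lesions, all in the patient's arm, analysed as independent.** If a fraction p of patients has two lesions and the rest have one, the mean number of lesions is 1 + p and the mean squared number is 1 + 3p. The design effect is D = 1 + ICC × [(1 + 3p)/(1 + p) − 1] = 1 + ICC × 2p/(1 + p), and the level is P(χ²₃ > 7.815/D). For example, p = 0.4 and ICC = 0.5 give D = 1 + 0.5 × 0.8/1.4 = 1.286, then 7.815/1.286 = 6.078, and a level of 10.8%.

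**3. Repeated lesions, allocated one by one in blocks.** This was simulated under the same assumptions.

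| Patients with two lesions | ICC | One arm, formula | One arm, simulated (N = 128, 192) | One by one, simulated (N = 128, 192) |
|---|---|---|---|---|
| 20% | 0.3 | 6.9% | 6.3%, 6.5% | 4.8%, 4.4% |
| 20% | 0.5 | 8.2% | 7.5%, 7.7% | 4.2%, 4.5% |
| 20% | 0.7 | 9.6% | 9.1%, 9.7% | 4.2%, 3.9% |
| 40% | 0.3 | 8.3% | 7.7%, 7.5% | 4.4%, 4.0% |
| 40% | 0.5 | 10.8% | 9.8%, 10.4% | 3.7%, 3.6% |
| 40% | 0.7 | 13.4% | 12.7%, 13.3% | 3.6%, 3.1% |

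Section 3.6 speaks of more than two lesions, so three was also simulated, in 40% of patients and with 200 lesions in all. At ICC 0.3, 0.5 and 0.7 the level is 12.5, 18.9 and 24.6% if lesions share an arm, and 3.3, 2.8 and 2.0% if they are allocated one by one.

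**4. Neither feature present.** With one lesion per patient and strata unrelated to pain, the simulated level is 4.9%.

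**The case against.** The strongest reply is that the inflated figures need a mixture of two readings. Choosing which lesion goes first has little purpose if all of a patient's lesions take the same arm, so section 3.6 points to one-by-one allocation, where the test is mildly conservative. If patients are the unit, as sections 3.7 and 3.9 suggest, there may be one rating each and the level is 5%. Inflation needs allocation by patient together with analysis by lesion. This objection stands. A reader might infer that the plan inflates the false-positive rate, and the documents do not support that. They merely fail to exclude it.

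It is also fair to say that ignoring the strata introduces no bias and costs little at 95% power. That stands too, and it limits the weight of the strata limb. It does not restore the stated level if the strata predict pain.

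A reader might also infer that the one-at-a-time risk-factor tests for section 2.2 are wrong, or that the covariate analysis fails to deliver a promised adjustment. Neither is supported. Section 2.2 asks only for factors associated with pain, marginal tests answer that, and section 4 promises no adjustment.

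Finally, clustering methods have their own faults. Simple cluster-robust errors in a rank model gave 5.1–7.3% here, and van Elteren alone does not handle within-patient correlation. Both points stand and shape the fix.

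**Conclusion.** The concern holds in a limited form. The planned group tests match the randomisation only if each participant contributes one lesion and the strata do not predict pain, and the plan says neither. Otherwise the primary test's level departs from 5%.

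- **Prognostic strata ignored:** about 3.4, 2.1 or 1.1% at an assumed R² of 0.1, 0.2 or 0.3, with no bias and about 0 to 2.5 points of power lost at the planned 95%.
- **Lesions allocated one by one (the more natural reading):** about 3 to 5%, assuming 20 to 40% of patients with two lesions and ICC 0.3 to 0.7.
- **Lesions sharing an arm but analysed as independent (less natural, not excluded):** about 6 to 13% on the same assumptions, and higher with three lesions.

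The sizes rest on these assumed inputs. The mismatch between design and analysis is in the text. It should be corrected before the sample size is calculated, because that calculation needs the same unit.

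**What to change.** 1. In section 3.6, name the strata. State whether the patient or the lesion is the unit of allocation and of analysis, and cover participants with exactly two lesions. Use the same unit in the section 3.5 calculation.
2. In section 4, pre-specify one primary analysis:
   - **Either** a single rank-based or ordinal model with arm and the randomisation strata and, where a patient contributes more than one lesion, a patient random effect or cluster-robust errors with a small-sample correction. The random-effect and small-sample-corrected versions were not simulated here, so their level should be checked at the final sample size. An ordinal model also needs its proportional-odds assumption checked.
   - **Or** only the first-allocated lesion per patient, with a stratified rank test (van Elteren for pairwise comparisons). Restricting to the first lesion held 4.3–5.2% in simulation.
3. Keep the planned unadjusted tests as a sensitivity analysis.
4. Optionally, label the section 2.2 results as unadjusted associations.

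The change needs no extra patients, visits or data. It costs slightly more analysis work, about half a point of pairwise power if the strata prove uninformative, and discarded lesions if only the first is used.

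### The only block size given equals the number of arms, so staff who know the earlier allocations in a stratum could deduce up to one allocation in four

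*Combined protocol and SAP*

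**What the plan says.** Section 3.6 (Randomization) gives one block size: "stratified permuted blocks of four". It names no stratification factor, does not vary block length, and does not say that the size is kept from staff. On concealment it says "these will be concealed in individual sealed envelopes with the aid of a research contributor". On order it says "Participants will be allocated in order of recruitment", with a rule for patients with several lesions: "lesions will have the more superiorly located lesion allocated first".

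Section 3.7 (Interventions) states "Patients will be split into 4 groups" and lists EMLA, aqueous ointment, ethyl chloride spray and no treatment.

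Section 3.8 (Study procedures) has the two creams "delivered via an unmarked syringe to achieve single blinding", without saying who is blinded. It describes no masking for the spray or no-treatment arms. Consent comes before allocation.

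The allocation ratio is not stated. Section 3.5 plans "an initial pilot study of ten patients" per group, which fits equal allocation.

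**The concern.** A permuted block cannot be shorter than the number of equally allocated arms, so four is the smallest block possible here and the most predictable. Once three different arms have been used in a block, the fourth is known. Sealed envelopes hide the content of the next envelope, but not what can be worked out from the ones already opened.

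Several features make this matter here. Section 3.2 recruits at a single centre, so the same small team may see successive allocations. Spray, cream under a dressing, and no treatment look different. Several lesions from one patient, allocated in turn, can reveal several places in a block at once. The primary outcome is a patient-reported pain score, and section 4 plans no covariate-adjusted model for the comparison between arms. If someone who could predict the next arm chose when, or in what order, to enrol patients, the resulting differences between arms would pass into the active-versus-control contrasts.

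**Working it through.** The documents give no predictability figure to reproduce, so the check enumerates the blocks.

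**Inputs.** Four arms (3.7). Block size four (3.6). Ratio 1:1:1:1 (assumed; it is the only ratio that puts all four arms in a block of four). Staff are assumed to know the block size, the block start and the earlier allocations in the stratum. A block then has 4! = 24 equally likely orders.

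**Case A: staff can tell all four arms apart.** At position j, 5 − j arms remain, so the best guess is right with probability 1/(5 − j).
- Best guess at positions 1 to 4: 1/4, 1/3, 1/2, 1. Mean = (0.250 + 0.333 + 0.500 + 1)/4 = 52.1%.
- Certain: 0, 0, 0, 1. Mean = 25%.
- At least one arm ruled out: 0, 1, 1, 1. Mean = 75%.

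**Case B: staff cannot tell EMLA from aqueous cream.** If the last place is spray or no treatment (probability 1/2), it is known exactly. If it is a cream, the guess between the two creams is right half the time.
- Best guess: 1/4, 1/3, 1/2, and 1/2 × 1 + 1/2 × 1/2 = 3/4. Mean = (0.250 + 0.333 + 0.500 + 0.750)/4 = 45.8%.
- Certain: 0, 0, 0, 1/2. Mean = 12.5%.
- At least one arm ruled out: 0, 1/2, 1, 1. Mean = 62.5%.
- The type of treatment (spray, cream or none) is always known at position 4. It is also known at position 3 when spray and no treatment came first (probability 2/4 × 1/3 = 1/6). Mean = (1 + 1/6)/4 = 29%.

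**Larger blocks.** Under full visibility the expected number of certain allocations is the expected length of the final run of one arm. For a block of 8 it is 1 + 1/7 = 8/7, and (8/7)/8 = 14.3%. For a block of 12 it is 1 + 2/11 + (2/11)(1/10) = 1.2, and 1.2/12 = 10.0%. The other entries for 8 and 12 come from exact enumeration or recursion.

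| Block | Visibility | Certain | Arm ruled out | Best guess right |
|---|---|---|---|---|
| 4 | all arms | 25% | 75% | 52.1% |
| 8 | all arms | 14.3% | 54.3% | 47.0% |
| 12 | all arms | 10.0% | 42.1% | 44.1% |
| 4 | creams masked | 12.5% | 62.5% | 45.8% |
| 8 | creams masked | 7.1% | 42.9% | 41.6% |

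For blocks of 8 and 12 in random order under full visibility, simulating 200 allocations with unknown boundaries and guessing the least-used arm gave 45.0% correct.

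**Illustrative bias.** Suppose patients placed on predicted active turns differ by d NRS points from those placed on predicted control turns. The documents give no value for d. The expected bias is d × (2P − 1), averaged over positions, where P is the chance of guessing active versus control correctly. Per 1 point of d, with blocks of four and all arms visible:
- Guessing the type with more places left: (0 + 1/3 + 1/3 + 1)/4 = 0.42.
- Guessing the type of a randomly picked unused arm: (0 + 1/9 + 1/3 + 1)/4 = 0.36.

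With blocks of 8 and 12 in random order these become about 0.30 and 0.27. With the creams masked from staff, the first rule gives about 0.25 for blocks of four and 0.19 for 8 and 12.

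**The case against.** A reader might infer that every fourth allocation is certain and that most allocations are visible to staff. The documents do not support either as a flat statement. Only two of the four arms, spray and no treatment, are plainly unmasked. Single blinding usually means that the patient alone is blinded, but section 3.8 does not say so, and case B applies if the unmarked syringe also masks staff. The blocks are stratified by unnamed factors, so the pattern runs within a stratum and has to be tracked there. The documents do not say that those who enrol patients open the envelopes or know the block size. The one-in-four figure is therefore an upper bound.

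A reader might also infer an expected bias of about 0.4 NRS points. That needs steering on every turn, full tracking, and an invented 1-point difference, and it changes with the guessing rule. With four assumed strata and counts kept only overall, a simulation gave 0.22 per point for blocks of four and 0.14 for 8 and 12.

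The protocol also has safeguards: consent before allocation, sealed envelopes, allocation in recruitment order, and a fixed lesion order (written only for patients with more than two lesions). These narrow the room for steering and protect the current envelope. They do not stop deduction from earlier envelopes, and they leave open when and in what order patients are approached.

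Lastly, larger blocks leave the best guess well above chance. That is correct, and it limits what the fix can claim.

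**Conclusion.** The point holds as a design weakness, not as evidence that allocation would be subverted. With four equally allocated arms, a fixed block of four is the most predictable permuted-block scheme available. Certain allocations lie between 12.5% (creams masked from staff) and 25% (all arms visible). Allocations with an arm ruled out lie between 62.5% and 75%. Best-guess success lies between about 46% and 52%, against 25% by chance.

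These figures rest on equal allocation and on staff who know the block pattern and the earlier allocations in the stratum. Less knowledge gives lower figures. Any bias in NRS points depends on an assumed steering difference and guessing rule, and should be shown only as an illustrative range. The weakness is avoidable at little cost, so the change is worth making before the start.

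**What to change.** In section 3.6, replace the fixed block of four with permuted blocks of randomly varying larger multiples of four, for example 8 and 12, within each stratum. Generate the list before the start. State that the person holding it keeps the block sizes from recruiting and operating staff until recruitment ends. Also state the allocation ratio, the stratification factors and who is blinded, because these decide which of the figures above apply.

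Under full visibility, best-guess success falls from 52% to about 45%, and certain allocations from 25% to between 10% and 14%. Withholding the sizes is useful in its own right and costs nothing. The 8 and 12 pairing is one reasonable choice among several.

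The cost is one regenerated list and somewhat more possible imbalance in incomplete blocks, including at the pilot. Unstratified blocks of four always balance at 40 patients (4 × 10). Blocks of 8 and 12 chosen with equal probability end exactly at 40 with probability 13/32 = 0.41. This comes from u(n) = ½u(n − 2) + ½u(n − 3), counting in fours, at n = 10. With four assumed strata, the simulated 95th-percentile gap between the largest and smallest arm at 40 patients rises from 3 to 5, in arms of about ten.

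### Lesion-level allocation in 3.6 conflicts with patient-level wording elsewhere, and section 4 names no unit of analysis and no method for several lesions from one patient

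*Combined protocol and SAP*

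**What the plan says.** Section 3.6 (Randomization) reads "Participants will be allocated in order of recruitment and in participants with more than two" and continues "lesions will have the more superiorly located lesion allocated first". It uses "stratified permuted blocks of four" and does not name the strata. The eligibility criteria in 3.3 and 3.4 do not limit the number of lesions per patient.

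Elsewhere the plan speaks of patients:

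- Section 3.5: "A formal sample size calculation will be performed after an initial pilot study of ten patients" per group. It refers to studies at "other non head and neck anatomical sites typically required less than 50 participants per" group, and adds a 10% margin for loss of participants.
- Section 3.7: "Patients will be split into 4 groups".
- Section 3.9: "each participant will be prompted to evaluate the pain they undergo". After the procedure, patients are also asked to score the overall experience.

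Section 2.2 adds "Analysis of risk factors associated with pain from local anaesthetic in the head and neck", and lists pathology, anaesthetic volume, size and site. These are properties of a lesion or its injection, not of a person.

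Section 4 names Kruskal-Wallis and Mann-Whitney (for group comparisons and covariate analysis), chi-squared and Spearman. It mentions patients when it justifies the per-protocol analysis, but does not say whether a data point is a patient or a lesion.

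**The concern.** An order for a patient's lesions serves a purpose only if further lesions are allocated too. The plan therefore foresees patients who contribute more than one allocation, and nothing says what happens to them at rating, sample size or analysis. Scores from one person tend to be alike, and all four named tests treat every score as independent.

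Three things are at stake. The error rates of the named tests depend on a sentence the plan does not contain. The analyst could choose the unit after seeing the data. And an experience score asked once per patient has no single arm to belong to when that patient's lesions received different arms.

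**Working it through.** **Inputs.** The documents give alpha 0.05, power 95%, four groups and blocks of four. They give no final sample size, share of multi-lesion patients or correlation, so there is no stated figure to reproduce. Assumed: equal allocation; 176 patients (4 × 44, in line with the mention of fewer than 50 per group); within-patient correlation 0.3 to 0.7; scores on 1 to 10, either roughly normal or floor-heavy (about 38% of untreated scores at 1). A patient's lesions take consecutive slots in blocks of four. The main runs had no strata. Each type I error case had 4,000 simulated trials, with standard error √(0.05 × 0.95 / 4,000) ≈ 0.003.

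**Type I error at nominal 0.05, lesions treated as independent**

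| Multi-lesion patients | Kruskal-Wallis, lesions allocated separately | Kruskal-Wallis, one arm per patient, all lesions analysed | Mann-Whitney on risk factor, half shared | Mann-Whitney on risk factor, fully shared |
|---|---|---|---|---|
| 10% with two | 0.040–0.049 | 0.057–0.074 | 0.050–0.056 | 0.052–0.064 |
| 30% with two | 0.033–0.053 | 0.070–0.104 | 0.053–0.071 | 0.060–0.084 |
| 40% with three | 0.019–0.040 | 0.114–0.249 | 0.067–0.100 | 0.099–0.146 |

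Half shared means a within-patient correlation of 0.5 in the factor. The listed factors are lesion-level, so full sharing is an upper bound. A factor not shared at all gave 0.045–0.054.

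**Why the directions differ.** When two lesions of one patient fall in different arms, the patient effect partly cancels in the comparison. The test ignores this and overstates the variance. When they share an arm, the variance of the arm mean is multiplied by 1 + ρ(Σk²/Σk − 1), with k lesions per patient. For 30% with two lesions and ρ = 0.5, Σk²/Σk = (0.7 + 0.3 × 4)/(0.7 + 0.3 × 2) = 1.9/1.3 = 1.46. The factor is 1 + 0.5 × 0.46 = 1.23, and P(χ² with 3 df > 7.81/1.23) = 0.096. Simulation gave 0.086–0.091.

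**Sensitivity to blocking and strata.** With correlation 0.6 and floor-heavy scores, separate allocation gave 0.048, 0.039 and 0.027 in the three rows without strata. With three strata drawn per lesion it gave 0.048, 0.048 and 0.039. A separate simulation of 200 lesions gave 0.019–0.045 with blocks and 0.045–0.057 when lesions were allocated independently without blocks. The conservatism comes from consecutive slots in one block and fades when lesions fall in different strata.

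**Precision.** At an effect of 0.6 SD (30% with two lesions, correlation 0.6, floor-heavy), Mann-Whitney on all lesions had power 0.81 and an ordinal model with a patient intercept 0.89–0.90. Using only the first lesion gave 0.70, against 0.71 with no multi-lesion patients. But 3.5 plans 95% power. With 44 per arm that corresponds to about 0.78 SD: Φ(0.78 × √(44/2) − 1.96) = Φ(1.70) ≈ 0.955. There, by normal approximation at correlation 0.6, ignoring versus using the patient effect gives 0.972 versus 0.985 at a 10% share, and 0.990 versus 0.999 at 30%. The gain is about 0.01.

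**Experience score.** Two consecutive slots lie in one block with probability 3/4, and the arms then always differ. Otherwise they differ with probability 3/4. So 3/4 + 1/4 × 3/4 = 15/16 of two-lesion patients receive two arms: about 9% of all patients at a 10% share (0.10 × 15/16) and 28% at 30%. With three equal strata drawn independently per lesion, the proportion is 1/3 × 15/16 + 2/3 × 3/4 = 0.81.

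**The case against.** The strongest reply is that the plan does name a unit. Sections 3.5 and 3.9 say patients or participants for sample size and rating, and 3.7 splits patients. A reader might infer that no unit is stated anywhere; the text does not support that. The defect is one sentence in 3.6 that conflicts with this wording, plus a unit of analysis left unstated. Separate allocation is itself an inference from the stated order.

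A reader might also infer from the third column of the table that the primary test carries a large false-positive risk. Those figures need every lesion of a patient to receive one arm and every lesion to be analysed. That is the less natural reading of 3.6, because a lesion order would then have little purpose. The highest value, 0.249, also needs 40% of patients with three lesions. On the natural reading the arm test is not materially inflated.

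Two further points stand. The loss of precision is small at the planned power. And no one model is required: a one-lesion rule fits the named tests, and patient-clustered standard errors are also valid.

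What the reply does not remove is the conflict itself. With one lesion and one rating per patient the problem would not arise, but the plan does not say that this is intended.

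**Conclusion.** The concern holds as an unreconciled conflict between 3.6 and sections 3.5, 3.7 and 3.9, with no unit of analysis and no method for correlated lesions in section 4. On the natural reading of 3.6, the arm test runs at about 0.02 to 0.05, nearer nominal with lesion-level strata, and forgoes a little precision. Risk-factor tests run at about 0.05 to 0.07 with two lesions per multi-lesion patient, and up to about 0.10 with 40% having three, when the factor is half shared.

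All these sizes rest on the assumed share, correlation and sample size. At a share of about 10% or less the effects are small. Confidence is medium: the textual conflict needs no assumption, but its size cannot be fixed from the documents. The change should be made because it is cheap and closes a choice that could otherwise be made after the data are seen.

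**What to change.** State one unit consistently in 3.5, 3.6, 3.7, 3.9 and section 4, by one of two routes.

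1. **Patient as unit.** Use one index lesion per patient (the first allocated) and one pain rating. This fits the existing patient wording and the named tests.
2. **Lesion as unit.** Take one pain rating per lesion and say in 3.5 whether the sample size counts lesions or patients. Analyse arms and risk factors with a method that allows for within-patient correlation: a patient random-intercept model, ordinal if feasible in the planned software, or patient-clustered standard errors. Add first-allocated lesion only as a sensitivity analysis. Say whether the experience score is asked per excision or once per patient. If once, do not assign it to an arm for patients whose lesions received different arms; report them descriptively.

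Under either route, change more than two to two or more in 3.6, because patients with exactly two lesions now have no order rule.

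The cost is wording only, with no new randomisation list. Route 1 leaves extra lesions unused, but costs no power against plan if the sample size counts patients. Route 2 needs a slightly more complex analysis. If the experience score is asked once per patient, it also takes mixed-arm patients out of that comparison (about 9% to 28% of patients at a 10% to 30% two-lesion share, without strata).
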